9.1.4. Follow-Up Phase

The Follow-up Phase will begin once the subject completes 39 cycles or 36 months (whichever occurs first) of active monitoring (Arm A) or daratumumab treatment (Arm B). Reasons for premature discontinuation of active monitoring or daratumumab treatment are listed in Section 10.2. Subjects who discontinue before PD must continue to have disease evaluations as described in Section 9.2, until study completion or confirmed PD (or other reasons as outlined in Section 10). If subjects have not progressed to MM, then no other treatment for SMM or MM is allowed during the study. Follow-up for first-line MM treatment (including the response to first-line MM treatment), second primary malignancies, and survival status will be obtained as specified in the Time and Events Schedule (Table 1). Survival will be followed until the end of the study and at a frequency of at least every 12 weeks until PD. After PD, survival is to be followed at least every 6 months, until the end of the study.

If PRO or survival information is obtained via telephone contact, then written documentation of the communication must be available for review in the source documents. If the subject has died, then the date and cause of death will be collected and documented in the eCRF.

9.2. Efficacy Evaluations

Disease assessments will be performed every 12 weeks until PD. A window of ± 7 days around the scheduled assessment date is allowed. For subjects with treatment delays, disease assessments should be performed at the scheduled disease assessment dates. They do not need to be repeated at the time of delayed daratumumab administration. Disease progression, if based on laboratory results only, must be confirmed by a consecutive assessment. A repeated investigation for confirmation of disease progression does not need to occur within a specified timeframe and could potentially occur on the same date (at a later timepoint). However, the original value meeting disease progression and the confirmation value must be consecutive (ie, no intermediate values that do not meet the definition of disease progression). It is not a requirement to have a repeat investigation if disease progression is based on at least 2 of the laboratory tests of Hb, calcium,

renal function and FLC at the same assessment date (eg, when Hb <10 g/dL and creatinine clearance <40 mL/min are present on the same day).

Disease assessments will be performed according to the Time and Events Schedule ([Table 1](#)). Disease evaluations scheduled for treatment days should be collected before study drug is administered. Disease progression to MM will be evaluated using the IMWG diagnostic criteria for MM ([Table 9](#)) (Rajkumar 2014²⁹). For subjects who discontinue active monitoring (Arm A) or daratumumab (Arm B) before PD, disease assessments should be performed according the Time and Events Schedule ([Table 1](#)) until study completion or confirmed PD (or other reasons as outlined in [Section 10](#)).

Per protocol Amendment 6, disease assessments will only be performed locally and locally diagnosed disease progression will be reported based upon study investigator review per IMWG criteria.

9.2.1. Assessment of Response

Per protocol Amendment 6, assessment of response will no longer be collected.

This study will use the IMWG consensus recommendations for MM treatment response criteria (Durie 2007⁷, Rajkumar 2011³¹, Kumar 2016¹⁴) presented in [Table 8](#). For quantitative immunoglobulin (QIg) at baseline, M-protein, and immunofixation measurements in serum and 24-hour urine, the investigator will use results provided by the central laboratory.

Table 8: International Uniform Response Criteria Consensus Recommendations

Response ^a	Response Criteria
Stringent complete Response (sCR)	
 • CR as defined below, plus • Normal FLC ratio, and • Absence of clonal PCs by immunohistochemistry, immunofluorescence^b or 2- to 4-color flow cytometry.
Complete response (CR) ^c	
 • Negative immunofixation on the serum and urine, and • <5% PCs in bone marrow.
Very good partial Response (VGPR) ^c	
 • Serum and urine M-component detectable by immunofixation but not on electrophoresis, or • ≥90% reduction in serum M-protein plus urine M-protein <100 mg/24 hours.
Partial response (PR)	
 • ≥50% reduction of serum M-protein and reduction in 24-hour urinary M-protein by ≥90% or to <200 mg/24 hours • If the serum and urine M-protein are not measurable, then a decrease of ≥50% in the difference between involved and uninvolved FLC levels is required in place of the M-protein criteria • If serum and urine M-protein are not measurable, and serum free light assay is also not measurable, then a ≥50% reduction in bone marrow PCs is required in place of M-protein, provided baseline bone marrow PC percentage was ≥30%.
Stable disease	
 • Not meeting criteria for CR, VGPR, PR, or symptomatic MM.

IMWG=International Myeloma Working Group; FLC=free light chain; MM=multiple myeloma; PC=plasma cell.

All response categories (CR, sCR, VGPR, PR) require 2 consecutive assessments made at any time before the institution of any new therapy and no known evidence of progressive or new bone lesions if radiographic studies were performed. VGPR and CR categories require serum and urine studies regardless of whether disease at baseline was measurable on serum, urine, both, or neither.

Radiographic studies are not required to satisfy these response requirements. Bone marrow assessments need not be confirmed.

^a Subjects will continue in the last confirmed response category until there is confirmation of progression or improvement to a higher response status; subjects cannot move to a lower response category.

^b Presence/absence of clonal cells is based upon the kappa/lambda ratio. An abnormal kappa/lambda ratio by immunohistochemistry or immunofluorescence requires a minimum of 100 plasma cells for analysis. An abnormal ratio reflecting presence of an abnormal clone is kappa/lambda of >4:1 or <1:2.

^c Clarifications to IMWG criteria for coding CR and VGPR in subjects in whom the only measurable disease is by serum FLC levels: CR in such subjects indicates a normal FLC ratio of 0.26 to 1.65 in addition to CR criteria listed above. VGPR in such subjects requires a >90% decrease in the difference between involved and uninvolved FLC levels.

9.2.2. Assessment of Disease Progression to Multiple Myeloma

Assessment of Progression to Multiple Myeloma (diagnostic progression)

During the study, disease progression will be measured according to the published international uniform diagnostic criteria for MM established by the IMWG (Rajkumar 2014²⁹) presented in Table 9. Progression evaluations for the primary endpoint/final analysis will be based on IRC review, in a blinded fashion, to objectively and consistently implement the IMWG diagnostic criteria for MM. The IRC responsibilities and procedures will be documented in a separate IRC charter.

Per protocol Amendment 6, disease progression will be evaluated locally by the study investigator using the IMWG criteria in Table 9. Disease progression will no longer be centrally evaluated by IRC. Local determination of disease progression should be reported in the eCRF.

Table 9: Diagnostic Criteria for Progression to Multiple Myeloma^f

Clonal bone marrow plasma cells $\geq 10\%$ or biopsy-proven bony or extramedullary plasmacytoma ^a PLUS 1 or more of the following:
• Calcium elevation (>0.25 mmol/L [>1 mg/dL] higher than ULN or >2.75 mmol/L [>11 mg/dL])
• Renal insufficiency (creatinine clearance ^b <40 mL/min or serum creatinine >177 μ mol/L [>2 mg/dL])
• Anemia (hemoglobin <10 g/dL [<6.5 mmol/L] or >2 g/dL [>1.25 mmol/L] lower than the lower limit of normal)
• Bone disease (one or more osteolytic lesions on LDCT, PET-CT, or CT) ^c
• Clonal bone marrow plasma cell percentage ^a $\geq 60\%$
• Involved: uninvolved serum free light chain ratio ^d ≥ 100
• >1 focal lesions ^e on MRI studies.

CT=computed tomography; LDCT=low-dose whole body computed tomography; MRI=magnetic resonance imaging; PET-CT=positron-emission tomography with computed tomography; ULN=upper limit of normal.

- Clonality should be established by showing κ/λ light-chain restriction on flow cytometry, immunohistochemistry, or immunofluorescence. Bone marrow plasma cell percentage should preferably be estimated from a core biopsy specimen (per IMWG criteria; however, bone marrow aspirate only is acceptable for this study); in case of a disparity between the aspirate and the core biopsy, the highest value should be used.
- Measured or estimated by validated equations.
- If bone marrow has less than 10% clonal plasma cells, then more than one bone lesion is required to distinguish from solitary plasmacytoma with minimal marrow involvement.
- These values are based on the serum Freelite assay (The Binding Site Group, Birmingham UK). The involved free light chain must be ≥ 100 mg/L. To avoid overcalling progression based on FLC ratio, the progression will be determined based on modified FLC criteria combining IMWG progression criteria with IMWG FLC ratio criteria, as described below.
- Each focal lesion must be 5 mm or more in size.
- Per protocol Amendment 6, progressive disease identification is based on local assessment only.

From Rajkumar 2014.²⁹

Free light chain criteria are designed for de novo diagnosis rather than for progression of SMM to MM. Prior experience suggests that therapy, especially with daratumumab, can in some instances preferentially reduce the uninvolved light chain, therefore suggesting progression despite actual therapeutic response/absolute reduction of the involved light chain. To avoid overcalling progression based on FLC ratio, the progression will be determined based on modified FLC criteria combining IMWG progression criteria with IMWG FLC ratio criteria:

- Serum FLC (involved/uninvolved) light chain ratio ≥ 100
- Involved light chain ≥ 100 mg/L
- Difference of involved – uninvolved light chain shows confirmed increase $\geq 25\%$ from lowest value (nadir)

Assessment of Biochemical Progression

Biochemical progression is defined as an increase of 25% from nadir value in any one of the following:

- Serum M-component (absolute increase must be ≥ 5 g/L)
- Urine M-component (absolute increase must be ≥ 200 mg/24 hours).

If the lowest M component was ≥ 50 g/L, then a serum M-protein increase ≥ 10 g/L is sufficient for biochemical progression.

In subjects without measurable serum and urine M-protein levels: the difference between involved and uninvolved FLC levels (ie, absolute difference) must be increased by 25% from nadir and the absolute increase must be >100 mg/L.

Biochemical progression is to be considered as an important risk factor to evolve to diagnostic progression and those subjects should be monitored closely. However, biochemical progression alone does not constitute a reason for discontinuing therapy.

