4.2. Exclusion Criteria

Any potential subject who meets any of the following criteria will be excluded from participating in the study:

1. Criterion amended per Amendment 2:
- 1.1 Multiple myeloma, requiring treatment, defined by any of the following:

- a. Bone lesions (one or more osteolytic lesions on low-dose whole body computed tomography [LDCT], positron-emission tomography with computed tomography [PET-CT] or CT). Subjects who have benign/post-traumatic bone lesions visible on screening images as well as previous imaging, may be considered for inclusion. Details (diagnosis, location, duration) on benign/post-traumatic pre-existing bone lesions that can be seen on the screening images (eg, old fractures) and were also present on previous imaging are to be reported in the CRF (see Section 9.1.2 and Section 9.2.7).
- b. Hypercalcemia (serum calcium >0.25 mmol/L [>1 mg/dL] higher than ULN or >2.75 mmol/L [>11 mg/dL]). Subjects who have clinically stable hypercalcemia attributable to a disease other than multiple myeloma (eg, hyperparathyroidism) may be considered for inclusion after a case by case review by the medical monitor (see Section 9.2.3).
- c. Renal insufficiency, preferably determined by creatinine clearance <40 mL/min measured or estimated using the MDRD ([Attachment 2](#)), or serum creatinine >177 μ mol/L. Subjects who have clinically stable renal insufficiency attributable to a disease other than multiple myeloma (eg, glomerulonephritis) may be considered for inclusion after a case by case review by the medical monitor (see Section 9.2.3).
- d. Anemia, defined as hemoglobin <10 g/dL or >2 g/dL below lower limit of normal or both; transfusion support or concurrent treatment with erythropoietin stimulating agents is not permitted. Subjects who have clinically stable anemia attributable to a disease other than multiple myeloma (eg, thalassemia, vitamin B12 deficiency, iron deficiency) may be considered for inclusion after a case by case review by the medical monitor (see Section 9.2.3). (Refer to [Appendix 18.1](#) for specific requirements for France.)
- e. Clonal BMPC percentage $\geq 60\%$
- f. Serum FLC ratio (involved:uninvolved) ≥ 100 (The involved FLC must be ≥ 100 mg/L)
- g. More than 1 focal lesion ≥ 5 mm in diameter by MRI

2. Primary systemic AL (immunoglobulin light chain) amyloidosis.
3. Criterion amended per Amendment 2:
 - 3.1 Exposure to any of the following

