to non-myeloma-related etiology; an appropriate workup should be performed. A kidney biopsy should be strongly considered when there is no increase in FLC or increase in urine Bence-Jones proteins. Measured or estimated glomerular filtration rates (according to the Modification of Diet in Renal Disease (MDRD) [Levey 2006¹⁹] formula; [Attachment 2](#)), as per local practice, are preferred over a fixed serum creatinine concentration. For subjects who discontinue treatment prior to PD, these measurements should continue to be analyzed every time disease assessments are performed.

Subjects who, at screening, have clinically stable renal insufficiency that has existed for several years and did not show any deterioration during the prior year, can be considered for eligibility as long as the causality of renal insufficiency is proven to be attributed to a disease other than multiple myeloma (eg, glomerulonephritis). Prior to screening, a case-by-case discussion with the medical monitor may occur with the inclusion of prior laboratory and biopsy results.

Hemoglobin

According to CRAB criteria, hemoglobin <10 g/dL or >2 g/dL lower than the lower limit of normal indicates progression to MM if it is not attributable to any other cause. Before PD is declared on the basis of anemia without other CRAB signs or symptoms, additional diagnostic tests (at a minimum, iron, ferritin, transferrin, manual smear review, Coombs testing, lactate dehydrogenase, vitamin B12, and folate) should be carried out to determine that there is no other underlying cause of anemia. Positive tests thought to at least partially explain the anemia should continue to be analyzed every time disease assessments are performed. In questionable cases, especially when there is anemia with no concomitant increase in measurable disease, a bone marrow examination must be performed to clarify the diagnosis of anemia before progression to MM can be diagnosed.

Subjects who, at screening, have anemia that has existed for several years and did not show any decline during the prior year, can be considered for eligibility as long as the anemia's causality is proven to be attributed to a disease other than multiple myeloma (eg, iron deficiency, Vitamin B12 deficiency, thalassemia). Prior to screening, a case-by-case discussion with the medical monitor may occur with the inclusion of prior laboratory results. (Refer to [Appendix 18.1](#) for specific requirements for France.)

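### Table 9 prints two unequal hemoglobin cut-offs as one: 10 g/dL is about 6.2 mmol/L, not 6.5, so whether the anemia limb of progression is met can depend on the reporting unit

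*Protocol*

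**What the plan says.** Table 9 in Protocol Section 9.2.2 defines progression to multiple myeloma. It requires a marrow or plasmacytoma condition plus at least one further finding. The anemia finding is "Anemia (hemoglobin <10 g/dL [<6.5 mmol/L] or >2 g/dL [>1.25 mmol/L] lower than the lower limit of normal". Each limb appears first in g/dL, with a bracketed mmol/L figure presented as its equivalent.

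Three other places give the absolute limit in g/dL only:

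- Section 4.2, exclusion 1.1d: "Anemia, defined as hemoglobin <10 g/dL or >2 g/dL below lower limit of normal or both".
- Section 9.2.3, Hemoglobin: "hemoglobin <10 g/dL or >2 g/dL lower than the lower limit of normal indicates progression to MM", provided no other cause explains it.
- Section 9.2, in its example of two laboratory criteria met together: "eg, when Hb <10 g/dL and creatinine clearance <40 mL/min are present on the same day".

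Neither document states a conversion factor or a governing unit for hemoglobin.

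Under Amendment 6, Section 9.2.3 moves these laboratory tests to local laboratories. Section 9.2.2 has the investigator apply Table 9 and ends independent review of progression: "Local determination of disease progression should be reported in the eCRF".

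**The concern.** A bracketed SI figure should be the same threshold in another unit. Here the mmol/L figure is the looser of the two, so the same blood value can meet the anemia limb when read in mmol/L and miss it when read in g/dL. Because the entry criterion uses g/dL only, some admissible baseline values already lie under the mmol/L figure.

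The stakes lie mainly with progression called by the investigator:

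- Under Protocol Section 10.2, disease progression ends active monitoring or study treatment.
- Under SAP Section 5.3.5.1 and Table 5, a subject who starts first-line therapy without progression on study treatment is censored for PFS2, while one who had progressed stays at risk. PFS2 rests on investigator assessment. It is in the tested hierarchy (SAP Section 5.1.1), with a final analysis still planned.
- PFS by investigator assessment is a sensitivity analysis of the primary endpoint (SAP Section 5.2.3) and may also be touched.

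**Working it through.** **Inputs.** From the Table 9 anemia row: 10 g/dL paired with 6.5 mmol/L, and 2 g/dL paired with 1.25 mmol/L. From exclusion 1.1d: 10 g/dL, or more than 2 g/dL below the lower limit of normal (LLN). Two inputs are not in the documents and are assumptions: a standard hemoglobin factor of 0.6206 mmol/L per g/dL (molar mass about 16,114 g/mol per heme subunit), and the LLN values below.

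**1. Can one factor reproduce the row?** No outside source is needed.

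- Ratio of the two limbs in g/dL: 10 / 2 = 5.0.
- Ratio of the two limbs in mmol/L: 6.5 / 1.25 = 5.2.
- Implied factors: 6.5 / 10 = 0.650 and 1.25 / 2 = 0.625 mmol/L per g/dL.

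A single conversion factor would give equal ratios, so the row contradicts itself.

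**2. Which pair fails?** With the assumed 0.6206, 2 g/dL = 1.241 mmol/L, which agrees with 1.25 up to rounding. But 10 g/dL = 6.206 mmol/L, not 6.5. Counting hemoglobin as a tetramer gives 1.55 mmol/L, so that does not explain 6.5 either. Other pairs in Table 9 agree. For creatinine, 2 mg/dL × 88.4 (the factor in Protocol Attachment 2) = 176.8, printed as 177 µmol/L. For calcium, with an assumed atomic mass of 40.078, 1 mg/dL = 0.250 and 11 mg/dL = 2.745 mmol/L, printed as 0.25 and 2.75.

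**3. Size of the gap.**

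| Factor (mmol/L per g/dL) | 10 g/dL in mmol/L | 6.5 mmol/L in g/dL | Gap, g/dL |
|---|---|---|---|
| 0.625 (the row's own) | 6.25 | 10.40 | 0.40 |
| 0.6206 (assumed) | 6.21 | 10.47 | 0.47 |

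**4. Where the gap changes a reading.** The limbs are joined by *or*, so the effective cut-off is the larger of the absolute limb and LLN minus the relative limb. The LLN limb overtakes 6.5 mmol/L at 10.40 + 2 = 12.40 g/dL (row's factor) or 10.47 + 2 = 12.47 g/dL (assumed factor).

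| LLN, g/dL | Cut-off read in g/dL | Cut-off read in mmol/L, as g/dL (0.625 / 0.6206) | Gap |
|---|---|---|---|
| 11.5 | 10.0 | 10.40 / 10.47 | 0.40 / 0.47 |
| 12.0 | 10.0 | 10.40 / 10.47 | 0.40 / 0.47 |
| 12.2 | 10.2 | 10.40 / 10.47 | 0.20 / 0.27 |
| 12.47 | 10.47 | 10.47 / 10.47 | none |
| 13.0 | 11.0 | 11.00 / 10.99 | none of substance |

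**5. Overlap with entry.** Exclusion 1.1d admits a hemoglobin at or above the larger of 10 g/dL and LLN − 2. Take 10.2 g/dL with LLN 12.0. It is 12.0 − 10.2 = 1.8 g/dL below the LLN, so it is admissible on hemoglobin and misses both g/dL limbs. In mmol/L it is 10.2 × 0.625 = 6.375 (6.33 with 0.6206), which is under 6.5. Only the hemoglobin limb is met; the remaining conditions still apply.

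**The case against.** The strongest reply accepts the arithmetic and disputes the consequence. Much of it stands.

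- *Primary PFS.* A reader might infer that the primary result was distorted by site-to-site differences in units. The documents do not support this. The primary analysis concluded before Amendment 6 (Amendment 6 rationale). It used blinded independent review supplied with central laboratory data (SAP Sections 1.2 and 5.2.1). BOD-PFS and the algorithm version of PFS used a validated algorithm. The units used by the central laboratory, the reviewers and the algorithm are not stated, so an effect there is neither shown nor ruled out.
- *Progression on the day of entry.* A reader might infer that an eligible subject could be called progressed at once, since Section 9.2 allows the confirming value to be taken the same day. That omits the safeguards. Table 9 needs the marrow or plasmacytoma condition. Section 9.2.3 requires other causes to be excluded, sets a minimum work-up before anemia alone counts, and requires a marrow examination in questionable cases. Section 9.2 requires a consecutive confirming value unless two laboratory criteria are met on one date. Section 10.2 adds confirmation by the medical monitor before discontinuation.
- *Working unit.* g/dL comes first in the row and stands alone in three other sections, so this may be only a faulty bracket. That is plausible, but no text says which unit governs, and an investigator reading a local report in mmol/L has only the bracketed figure to apply.
- *Frequency.* Nothing shows how many sites report in mmol/L or how many subjects fall in the band. Any count of affected events would be a guess.

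The safeguards reduce miscalls. They do not turn two thresholds into one.

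**Conclusion.** The point holds as an internal contradiction in a decision threshold. The two absolute figures in the Table 9 anemia row differ by 0.40 g/dL on the row's own factor and by 0.47 g/dL on the assumed standard factor, and the mmol/L version is the looser. The difference matters only where the LLN is below about 12.4 to 12.5 g/dL. There, a hemoglobin of 10.0 to about 10.4 g/dL can be admissible at entry and yet meet the mmol/L limb. The documents give no LLN, so the reach is unknown.

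Exposure is clearest for local investigator calls after Amendment 6 and the discontinuation and PFS2 rules that depend on them, and possible for the investigator-assessed PFS sensitivity analysis. No effect on independently reviewed primary PFS is shown, and no difference between arms is shown. The figure should be corrected because it is wrong as printed and cheap to correct, not because a distorted result has been demonstrated. Which cut-off is clinically right is not judged here.

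**What to change.** - Reconcile the two absolute hemoglobin figures in Table 9 with each other and with exclusion 1.1d, the Section 9.2 example and Section 9.2.3, so that both units express one threshold. State the conversion factor.
- Instruct sites to convert hemoglobin to one stated unit before applying the threshold.
- Establish and record which unit the independent reviewers and the algorithm used.
- List any anemia-based progression with a hemoglobin between the two printed cut-offs (about 6.2 to 6.5 mmol/L, or 10.0 to 10.5 g/dL) and check whether the call depended on the unit.

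The cost is one reconciled table entry, a short site instruction, a look at the review and algorithm specifications, and a limited data query. Calls made after Amendment 6 may need a query to the site, because the amendment summary says that local laboratory results are no longer reported to the sponsor. No new assessments are needed.
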